## 2.2 Overview of Study Design

This will be a randomized, unblinded study of six times per week nocturnal home hemodialysis versus three times per week conventional home hemodialysis. A target of 90 patients will be enrolled into this study with equal allocation in each arm, stratified by Clinical Center and diabetic status. All patients will be assessed for suitability for nocturnal home hemodialysis using a standardized method prior to patients entering the baseline portion of this protocol. The minimum dialysis dose in the conventional home arm will be an equilibrated Kt/V of 1.1.In the nocturnal arm there will be a minimum prescription of six hours per session for six days per week AND a minimum achieved standard Kt/V of 4.0. Patients will be followed for 12 months.

Because no previous randomized trials of nocturnal dialysis have been conducted, the first calendar year after the initiation of enrollment has been designated as a "Vanguard" phase during which feasibility of randomization and conduct of the interventions will be evaluated. If pre-defined benchmarks for establishment of feasibility are achieved during the Vanguard phase, the trial will proceed to its primary objective of determining if 6 times per week nocturnal hemodialysis results in clinically significant improvements in physiological, health-related quality of life (HRQL) and functional outcomes, as compared with three times per week conventional home hemodialysis.

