## 2.3 Study Timeline

This trial will be carried out in 5 phases. The first 24 months (Phase I) will be used to finalize the study protocol, secure Institutional Review Board approval, and create procedures manuals, data collection forms, program the trial database and train study personnel (Pre-trial planning). Subject enrollment then began under a Vanguard phase (Phase 2a) that was designed to last for 12 months. Four months into this Vanguard phase, it was determined that it would be difficult to meet recruitment goals with the current protocol. Thus, with NIH and DSMB input, a revised protocol was developed and implemented. Enrollment in the original protocol (V 2.1) of patients was frozen on 9/27/06 and was reopened using the revised (V 3.0) protocol once two of the eight clinical centers received local IRB approval for the revised protocol. The first 12 months of the recruitment period with the revised protocol (V3.0) (Phase 2b) will be referred to as the "New Vanguard" phase

of the trial. This New Vanguard phase will be used to identify process factors that can be modified to improve recruitment and adherence, and subsequently to evaluate the feasibility of recruitment and conduct of the interventions according to pre-established benchmarks. If the New Vanguard phase demonstrates feasibility, recruitment will continue over a further 16 months (Phase 3) of the 29 month accrual period of the revised protocol. Each subject will be treated and followed for 12 months and followed for up to 2 or more months for limited data collection (Phase 4). The last three months will be allocated to final data analysis, reporting of the results, and preparing of the trial database for archival (Phase 5).

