### 9.5 General Analytic Strategy for Quantitative Outcomes

The following analytic strategy will be employed for quantitative outcomes, including each of the main secondary outcomes with the exception of the rate of non-access hospitalization or death. The main analysis for each outcome will evaluate the treatment effect on the change from baseline to 12 months. For outcomes evaluated monthly (serum albumin and pre-dialysis phosphorus) the 12 month value will be averaged over the Months 10, 11, and 12 assessments for increased statistical power. For each outcome with multiple follow-up assessments (including the PHC, serum albumin, Beck Depression Inventory, Trailmaking Test B, and pre-dialysis phosphorus), an additional analysis will be conducted to evaluate the change from baseline to Month 4, where the Month 4 value is taken as the average value over months 3, 4, and 5 for serum albumin and pre-dialysis phosphorus. The analysis of change to 4 months will evaluate short term effects, while the analysis of change to 12 months will evaluate longer-term effects. The 4-month comparison is also intended to evaluate treatment effects prior to significant attrition. The "basic model" to be used for quantitative outcomes is:

$$\Delta \mathbf{Y}_{t} = \beta_{0t} + \beta_{1t} \operatorname{Trt} + \beta_{2t} \mathbf{Y}_{0} + \Sigma \gamma_{it} \mathbf{S}_{i} + \Sigma \delta_{it} \mathbf{F}_{i} + \varepsilon_{t}, \quad (\text{Basic Model})$$

where  $\Delta Y_t$  denotes the change in the response variable from baseline to time t, Trt is an indicator variable for the daily treatment intervention,  $Y_0$  is the baseline value of the response variable, the  $S_i$  are indicator variables for the Clinical Centers, the  $F_i$  are the following six pre-specified baseline covariates (age, race, years of dialysis, diabetic status, baseline serum albumin, and

FHN Nocturnal Protocol Version 3.3: October 15, 2008

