baseline GFR), and the  $\varepsilon_t$  are random residuals at t = 4 and 12 months. The primary focus of the model will be to estimate the treatment effect  $\beta_{1t}$  as accurately as possible; the remaining terms are included to reduce residual variability and reduce bias from missing data. The model will be fit by restricted maximum likelihood [Harville, 1977] assuming an approximate normal distribution and with an unstructured covariance matrix for the residuals at the two time points. The change in the LV mass from baseline to its single follow-up assessment at 12 months will be analyzed by restricting the basic model to one time point, which simplifies to traditional analysis of covariance.

The target sample size of 90 patients is sufficient that inferences for the fixed effect terms in these analyses will remain valid with moderate departures from normality [Verbeke, 1997]. However, standard diagnostics will be performed and simulations conducted to address this issue, and modifications to the model will be made if necessary. In addition to evaluating the effects of the treatment interventions on LV mass, in grams, the effects of the interventions on the percentage change in LV mass will also be considered in secondary analyses.

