Estimated Detectable Effect Sizes for 80% or 90% Power for the Primary Outcomes

 As described in the text, under the Hochberg procedure the statistical power for each of the two primary outcomes depends in part on the effect size for the other outcome. Thus, the minimum detectable effect on the LV mass-Mortality composite is evaluated assuming treatment effects on the change in the PHC of either 0, 2.28 (corresponding to 25% of the estimated standard deviation of the change in the PHC score after covariate adjustment), or 4.56 units (corresponding to 50% of one standard deviation). Similarly, the treatment effects on the PHC-Mortality composite are evaluated assuming effects of either 0, 6 (25% of 1 SD) or 12 g on the

change in LV mass. The simulation results indicate the above calculations are accurate if the correlation between the change in LV mass and the change in the PHC score is between 0 and +0.5.

Table 15 provides the estimated minimum detectable effect sizes for each of the quantitative main secondary outcomes under the following assumptions: a) measurements obtained at 12 months in 80% of patients for each outcome, b) the standard deviations of the changes in each outcome (with covariate adjustment) are as indicated in Table 15, c) two-sided significance levels of 0.05 are applied to each outcome, without adjustment for multiple tests, d) utilization of the parametric analysis of changes with covariate adjustment outlined in Section 9.5. The power calculations do not take into account information provided by the 4 month measurements for patients with missing data at 12 months; thus, in this respect the values are slightly conservative. As in Table 14, the minimum detectable effects are provided both overall (without parentheses), and among the assumed 95% of patients who complete the post-randomization component of the nocturnal training program (with parentheses), assuming no treatment effect among those not successfully completing the training program.

#### Table 15

Estimated Detectable Effect Sizes for 80% or 90% Power for the Main Secondary Outcomes

Outcome Variable	Assumed SD of 1 Yr Change	80% power	90% power
PHC (points)	8.310	5.54 (5.83)	6.40 (6.74)
LV mass (g)	24.00	16.0 (16.8)	18.5 (19.5)
Average Albumin (g/dL)	0.296	0.198 (0. 208)	0.229 (0.241)
Average serum phosphorus (mg/dL)	1.636	1.08 (1.14)	1.26 (1.33)
Beck Depression Inventory (1 SD) 	-	0.67 (0.71)	0.77 (0.81)

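### Table 15 makes no allowance for the centre and covariate terms of the model it cites; at its printed SDs, power is about 71–73% and 83–85% rather than 80% and 90%

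*Protocol*

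**What the plan says.** Protocol Section 9.11 lists four assumptions for Table 15. Month-12 values are taken to be available for four patients in five. On the SDs it says that "the standard deviations of the changes in each outcome (with covariate adjustment) are as indicated in Table 15". Every outcome is tested two-sided at the 5% level with no multiplicity correction. The analysis is given as "d) utilization of the parametric analysis of changes with covariate adjustment outlined in Section 9.5".

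The target is 90 patients allocated 1:1 (Section 2.2). The Basic Model of Section 9.5 contains treatment, the baseline value of the outcome, six named baseline covariates, and terms that "are indicator variables for the Clinical Centers". Section 9.5 does not give the number of centres. Section 2.3 refers to "two of the eight clinical centers received local IRB approval", while Table 2 lists twelve sites.

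Section 9.11 says that the SDs for PHC, albumin and phosphorus were estimated from the HEMO Study after controlling for the baseline value and the covariates. The LV mass SD of 24 g appears both in Table 15 and, as an SD without adjustment, among the assumptions for Table 14. The Beck Depression Inventory and Trailmaking rows are in SD units because no pilot SD was available. The section describes the Table 15 values as slightly conservative in one respect only, namely that the 4-month data are not used. Archive notes in Sections 2.7 and 9.9 record that the prognostic covariates were later dropped from the analyses.

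**The concern.** An adjusted analysis has a gain and a cost. The gain is a smaller residual SD. The cost is a few lost degrees of freedom and, more importantly, a larger variance of the treatment coefficient, because the fitted terms are never perfectly balanced between the arms. The cost is negligible when terms are few relative to patients. Here there is one nuisance term for every four or five observed patients. If Table 15 carries the gain through the SD and leaves out the cost, the stated power is not that of the stated analysis. Null results on outcomes that the Protocol treats as the lead measures of their domains would then be read against a sensitivity that the trial does not have.

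**Working it through.** **Inputs.** 90 patients, 80% measured: 72, or 36 per arm. Two-sided alpha 0.05. SDs from Table 15. Terms beyond intercept and treatment: 7 centre indicators (8 centres) or 11 (12 centres), plus the baseline value and six covariates, giving 14 or 18.

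**Step 1: reproduce Table 15.** SE = SD × √(2/36). For PHC, 8.310 × 0.2357 = 1.959. The noncentrality at the printed effects is 5.54/1.959 = 2.83 and 6.40/1.959 = 3.27. With 70 df the power is 79.7% and 89.7%. Over all rows, power at the printed effects is 78.9–80.1% and 89.7–89.9%. Solving for the effect gives PHC 5.56/6.44, LV mass 16.07/18.59 g, albumin 0.198/0.229, phosphorus 1.095/1.268 and 0.670/0.775 SD. The table is therefore a two-group comparison with no allowance for fitted terms.

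**Step 2: the Section 9.5 model at the same SDs.** Residual df are 72 − 2 − 14 = 56 (8 centres) and 72 − 2 − 18 = 52 (12 centres). The variance of the treatment coefficient was obtained by simulation: 90 patients spread evenly over the centres, permuted blocks within centre and diabetic status (the strata of Section 2.9), 72 observed at random, and covariates independent of each other. Assumptions not in the Protocol: 40% diabetic, block sizes of 2 and 4, and no variance explained by centre beyond the printed SD. Power is noncentral t on the realised variance and df.

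| Model and centres | Variance inflation | Power at printed 80% / 90% PHC effect | PHC detectable at 80% / 90% |
|---|---|---|---|
| Full, 8 | 1.16 | 73.4% / 84.7% | 6.01 / 6.96 |
| Full, 10 | 1.18 | 72.5% / 83.9% | 6.07 / 7.04 |
| Full, 12 | 1.21 | 71.5% / 83.1% | 6.14 / 7.12 |
| Centre + baseline only, 8 | 1.06 | 77.3% / 87.9% | 5.73 / 6.63 |
| Centre + baseline only, 12 | 1.09 | 75.9% / 86.7% | 5.83 / 6.75 |

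Repeat runs agreed to about half a point. A hand check for 8 centres: 2.83/√1.158 = 2.63; less the critical value 2.00 leaves about 0.63, which is a power of about 73%.

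**Step 3: where the loss comes from.** With 52 df but no variance inflation, power would still be about 79.3% / 89.4%. Nearly all the loss is chance imbalance.

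**Step 4: other rows.** The full-model detectable effects are 0.723–0.739 SD at 80% power. Albumin: × 0.296 = 0.214–0.219 (printed 0.198). Phosphorus: × 1.636 = 1.18–1.21 (printed 1.08). LV mass: × 24 = 17.3–17.7 g (printed 16.0), if 24 g really is the residual SD.

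**Step 5: gain against cost for PHC.** Section 9.11 gives 9.12 unadjusted and 8.310 adjusted: (8.310/9.12)² = 0.83, a 17% variance reduction. Multiplying by the inflation gives 0.83 × 1.158 = 0.96 to 0.83 × 1.208 = 1.00. The cost absorbs most or all of the gain that the table credits.

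**The case against.** The strongest reply is that entering a residual SD into a two-group formula is the usual planning approximation, and that no entry is miscalculated. That is correct. A reader might infer that Table 15 ignores covariate adjustment altogether, but it does not: adjustment enters through the SD. What is left out is its cost, and the approximation is optimistic with this many terms.

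Second, the recomputed power is conditional. Centre is charged in full and credited with nothing, although albumin and phosphorus are mostly local-laboratory values and some between-centre variance is plausible. This stands as a limit. To restore the printed power under the full model, however, centre would have to explain about 14–18% of residual variance, and the Protocol gives no basis for that.

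Third, LV mass takes no adjustment gain, since 24 g is also the unadjusted SD. Covariates explaining about 14–18% of variance would offset the cost in that row. The two rows in SD units depend on which SD is meant. Both points stand.

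Fourth, the archive notes say that the covariates were dropped. With centre and baseline terms only, power at the same SD is about 76–77%. But the SDs for PHC, albumin and phosphorus were estimated after controlling for those covariates, so they would need revising as well.

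Fifth, the 4-month data are a real offset. If they are worth three extra patients (75 instead of 72, an assumption), power is about 75.5% with 8 centres and 73.6% with 12.

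Two stronger readings lack support. One is that the shortfall arose because a model designed for 250 patients was carried over to 90. The Executive Summary records the reductions in target, but no earlier power section is shown. The other is that Section 9.5 vouches for the model at this size with "The target sample size of 90 patients is sufficient that inferences for the fixed effect terms in these analyses will remain valid". That sentence goes on to concern departures from normality, not power or the number of terms.

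**Conclusion.** The point holds in conditional form. Table 15 states the power of a 36-versus-36 comparison while naming a model with 14–18 further terms. At the printed SDs, with 8–12 centres and no between-centre variance, the power of that model is about 71–73% where 80% is stated and 83–85% where 90% is stated. Detectable effects are about 8–11% larger. This is firmest for PHC, albumin and phosphorus, and open for LV mass and the two rows in SD units. These are not the true power figures in any absolute sense, because the Protocol fixes neither the number of centres nor the between-centre variance.

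A reader might carry the shortfall over to the primary analysis. The Protocol does not support that: Table 14 rests on an unadjusted log-rank test with unadjusted SDs. The consequence is confined to how sensitive the main secondary analyses are said to be.

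**What to change.** Recompute Table 15 for the model that will actually be fitted:

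- State the assumed number of centres, reconciling the eight of Section 2.3 with the twelve of Table 2.
- Use SDs that match the fitted terms. If the covariates are dropped, replace the covariate-adjusted SDs. For LV mass, say whether 24 g is a residual or a raw SD, and for the two rows in SD units say which SD is meant.
- Include the variance inflation and the residual df, and print the less favourable detectable effects. Under the full model these are, for PHC, about 6.0–6.2 at 80% power and 7.0–7.2 at 90%. The values in parentheses follow on division by 0.95.
- Keep the remark on the unused 4-month data, but present it as a partial offset to this cost.

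The cost is one simulation and a revised table. No patients need to be added and the Section 9.5 model can stay as it is.

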## 10. Safety and Monitoring

# 10.1 Data Safety and Monitoring Board

The External Advisory Committee/Data Safety and Monitoring Board (DSMB) will meet regularly to review the safety of the participants during the course of the study. In addition, the DSMB will monitor the operational progress of the trial and evaluate interim analyses of treatment efficacy performed by the Data Coordinating Center.

The specific activities of the DSMB will vary during the course of the trial. Prior to the start of the trial, the DSMB will review and approve the protocol and template informed consent form. During the Vanguard phases, the DSMB will review quarterly reports summarizing the operational conduct of the study, including analyses of recruitment, success of the training program for nocturnal dialysis, retention, adherence, adherence, and quality control. The quarterly reports will include specific assessments of the success of the trial in meeting the pre-designated benchmarks for the Vanguard phases. The DSMB will also review quarterly tabulations of stop points, action items, and adverse events. The DSMB will meet by teleconference after receiving the second quarterly report, and more often if necessary, to verify the safety of the trials and provide feedback regarding the operational issues.

After the completion of the Vanguard phases, the DSMB will meet in person to determine whether the trial should proceed to completion based on the extent to which the benchmarks established for the Vanguard phase are met. Depending on the success of the Daily HD trial and its parallel Nocturnal HD trial in meeting their operational goals, the DSMB may recommend a revision of the target sample sizes and reallocation of resources between the two trials.

After the New Vanguard Phase, subsequent interim reports will be provided to the DSMB at months 15, 21, 27, and 33. These reports will include summaries of the operational progress of the trial and patient safety, as well as interim analyses of the effects of the treatment interventions on the primary and main secondary endpoints at 4 and 12 months follow-up. The DSMB will meet by teleconference following distribution of the month 15 and month 27 reports, and will hold face-to-face meetings following the month 21 and month 33 reports. If necessary, additional teleconferences and face-to-face meetings will be scheduled.

# **10.2 Definition and Reporting Safety-Related Adverse Events**

A Standards of Care/Clinical Management Committee will oversee that standards of care are being met (see Section 3.4.2). A blinded Outcome Committee will monitor and investigate adverse events that will be reported to the DSMB. The following adverse events will be reported monthly by the DCC to the Outcomes Committee (see Section 7) who will investigate them and complete an assessment of their seriousness and relatedness to the randomized therapy. The frequency of these adverse events and detailed assessments will be reviewed by the DSMB quarterly. The adverse events to be handled in this way are:

- i) all deaths which occur during the hemodialysis session itself
- ii) all deaths which occur at home
- iii) all hospitalizations which result from an event occurring during or immediately after the HD session

 iv) any premature discontinuation of the HD session for medical or technical reasons (these include but are not limited to, blood line disconnection, air embolism, leakage of dialysate into blood line, etc.)

Safety analyses presented at annual DSMB meetings will include summary reports of frequency and differences between treatment groups for each of the following:

- i) deaths
- ii) hospitalizations
- iii) vascular access failures (primary and secondary)

#### 10.3 Stopping Rules

A formal stopping rule for efficacy will not be used because none of the intermediate outcomes are judged to be sufficiently definitive to warrant early termination of the trial, and because it is unlikely to be feasible to switch a large proportion of the patients in the conventional arm to nocturnal dialysis therapy until after the scheduled termination of the trial. However, to assist the DSMB in interpreting results from multiple looks at the data, the DCC will provide thresholds for statistical significance for each intermediate outcome based on the O'Brien-Fleming rule.

